12.7.5.4 Drug of Abuse Screen

Drug of abuse screen is planned to be collected at Screening and Period 1 Day 1 H0.

A by-patient listing presenting all THC measures along with urinary drug screen results will also be provided.

12.7.5.5 Pregnancies

Any reported positive pregnancy results or reported pregnancies will be listed.

12.7.5.6 Examination of Oral Mucosa

Based on the Safety Analysis Set, results of oral mucosa examination (normal, abnormal NCS and Abnormal CS) planned to be performed at Screening, Day 1 H0, Day 15 and D21 of each period and during the follow-up visit will be described by treatment arm according to baseline status.

Each patient presenting at least one abnormal assessment will be listed.

12.7.5.7 Covid-19 Impact

The impact of COVID-19 on each visit will be summarized by treatment arm and a by-patient listing presenting patients impacted by COVID-19 during the conduct of the trial will be provided.

14.0 Glossary of Abbreviations

Glossary of Abbreviations:	
11-COOH-THC	11-carboxy- Δ^9 -tetrahydrocannabinol
11-OH-THC	11-hydroxy- Δ^9 -tetrahydrocannabinol
7-COOH-CBD	7-carboxy-cannabidiol
7-OH-CBD	7-hydroxy-cannabidiol
ADaM	Analysis dataset model
ADL	Activity of Daily Living
AE	Adverse event
AESI	Adverse events of special interest
ATC	Anatomic Therapeutic Class
ET visit	End of Treatment visit
ALT	Alanine aminotransferase
ALP	Alkaline phosphatase
AST	Aspartate aminotransferase
BLQ	Below Limit of Quantification
BDZ	Benzodiazepine
BMI	Body Mass Index
bpm	Beats per minutes
CBD	Cannabidiol
CDF	Cumulative distribution function
CFB	Change from baseline
CI	Confidence interval
CRF	Case report form
CS	Compound symmetry
CS	Clinically significant
CSR	Clinical study report
C-SSRS	Columbia-Suicide Severity Rating Scale
CTCAE	Common Terminology criteria for adverse events
CTMS	Clinical Trial Management System
CV	Coefficient of variation
D	Day
DBP	Diastolic blood pressure
DILI	Drug-Induced Liver Injury
DISH	drug-induced serious hepatotoxicity

DMD	Disease Modifying Drug
DRESS	Drug reaction with eosinophilia and systemic systems
ECG	Electrocardiogram
eCRF	Electronic case report form
EDC	Electronic data capture
eDiary	Electronic diary
eGRF	Estimated Glomerular filtration rate
FAS	Full Analysis Set
FU	Follow-up
GEE	Generalized estimating equation
GGT	Gamma-glutamyl transferase
GW	GW Pharma Ltd / GW Pharma Limited
H	Hour
HLGT	High Level Group Term
HLT	High Level Term
HR	Heart rate
hrs	hours
ICF	Informed consent form
ICH	International Council for Harmonisation
IES	Intercurrent event(s) strategy
IMP	Investigational medicinal product
INR	International normalized ratio
IPD	Important protocol deviation
IRT	Interactive response technology
kcal	Kilo calories
KM	Kaplan-Meier
KR	Kenward-Roger
KR2	Kenward-Roger method (e.g., KR2, 2009 version)
LLMT	Lower Limb Muscle Tone
LLMT-4	Lower Limb Muscle Tone-4
LLMT-6	Lower Limb Muscle Tone-6
LLMT-10	Lower Limb Muscle Tone-10
LLN	Lower Limit of Normal
LME	Linear mixed-effects
LS mean	Least square mean

LSMD	Least square mean difference
M	Month
MAR	Missing at Random
MAS	Modified Ashworth Scale
Max	Maximum
MCMC	Markov Chain Monte Carlo
MDRD	Modification of Diet Renal Disease
MedDRA	Medical Dictionary for Regulatory Activities
MHP	Mobile Health Platform
MI	Multiple Imputation
Min	Minimum
MNAR	Missing Not At Random
MS	Multiple sclerosis
msec	millisecond
MSSS-88	Multiple Sclerosis Spasticity Scale
NC	Not Calculated
NCS	Not Clinically significant
NRS	Numerical Rating Scale
OR	Odds ratio
P	Period
PD	Pharmacodynamic
PK	Pharmacokinetic
PLS	Population-level summary
PP	Per Protocol
PRA	Pharmaceutical Research Associates
PRN	pro re nata (meaning as-needed)
PRO	Patient reported outcome
PSO	Predictive Study Operations
PT	Preferred term
Q1	First Quartile / Quartile 1
Q3	Third Quartile / Quartile 3
QTc B	QT corrected Bazett's formula
QTc F	QT corrected Fridericia's formula
SAE	Serious adverse event
SAP	Statistical analysis plan

SBP	Systolic Blood Pressure
SD	Standard deviation
SDTM	Study data tabulation model
SE	Standard error
SI	Standard International
SOC	System organ class
T25FW	Timed 25-Foot Walk
TBL	Total bilirubin
TEAE	Treatment-emergent adverse event
THC	Δ^9 -Tetrahydrocannabinol
UK	United Kingdom
ULN	Upper limit of normal
UN	Unstructured
WHO-DD	World Health Organization-Drug Dictionary
Y	Year

Appendix 1 Classification of Protocol Deviations

List of Important Protocol Deviation Category

Number	IPD category
01	Inclusion criteria
02	Exclusion criteria
03	Study drug
04	Assessment safety
05	Efficacy/pharmacodynamic endpoint
06	Visit window
07	Prohibited co-medication
08	Others

List of Major Important Protocol Deviations

Number	Major IPD category	Major IPD criteria
01	Inclusion criteria	Patient was not diagnosed with any disease subtype of MS, by revised 2017 McDonald criteria, for at least 12 months prior to Visit 1.
02	Inclusion criteria	Does not have a MAS untransformed score of at least 2 in 2 or more of six muscle groups (right knee flexors, left knee flexors, right knee extensors, left knee extensors, right plantar flexors, or left plantar flexors) at Visit 1.
03	Inclusion criteria	Subject was not receiving optimized treatment with at least 1 oral antispasticity drug (baclofen, tizanidine, and/or dantrolene) that has been stable for at least 30 days prior to Visit 1.
04	Exclusion criteria	Has taken nabiximols, cannabis, or a cannabis-derived product for medicinal or recreational purposes in the 30 days prior to Visit 1 and unable to abstain for the duration of the trial.
05	Exclusion criteria	Did not respond adequately to treatment with nabiximols or another cannabis-based medication if exposed at any time before the 30-day period prior to Visit 1.
06	Exclusion criteria	Any concomitant disease or disorder that has spasticity-like symptoms or that may influence the patient's level of spasticity.
07	Exclusion criteria	Has had a relapse of MS within the 60 days prior to Visit 1.
08	Exclusion criteria	Clinically suspected to have a contracture in one of the muscle groups of the lower limbs, preventing assessment with the MAS.
09	Exclusion criteria*	Has any other clinically significant disease or disorder (including seizure disorder) that, in the opinion of the investigator, may put the patient at risk because of participation in the trial, influence the interpretation of trial results, or may affect the patient's ability to take part in the trial. For certain disorders, determined with medical monitor
10	Study drug	Subject taking more than 13 sprays per day at any time during each treatment phase.
11	Study drug	Patient randomized but not exposed to study drug.
12	Study drug	Subject not receiving at least 1 spray in the morning on the last day during maintenance phase.
13	Study drug	Subject receiving IMP during the washout period.
14	Study drug	Subject not exposed to IMP during at least 1 day during titration or the maintenance phase.
15	Study drug	Subject not exposed to IMP during at least 1 day in either treatment period.
16	Study drug	Patient receiving a kit number not allocated by IXRS which is not the treatment he/she was allocated to by IXRS during this period.
17	Efficacy endpoint	Missing evaluable MAS LLMT-6 pre-dose assessment.
18	Efficacy endpoint	Missing evaluable MAS LLMT-4 pre-dose assessment.
19	Efficacy endpoint	Missing evaluable MAS LLMT-6 at endpoint. (D21 or Day 51)
20	Efficacy endpoint	Missing evaluable MAS LLMT-4 at endpoint. (D21 or Day 51)
21	Visit window	Wash-out duration of less than 7 days.
22	Visit window	During maintenance phase: Visit 4 occurred +/- 2 days out of window

Number	Major IPD category	Major IPD criteria
		Visit 5 occurred +/- 3 days out of window Visit 6 occurred +/- 2 days out of window Visit 8 occurred +/- 2 days out of window Visit 9 occurred +/- 3 days out of window
23	Prohibited co-medication	Patient taking antipsychotic medication at any time during the trial.
24	Prohibited co-medication	Patient taking benzodiazepine on an as needed (PRN) basis during the trial.
25	Prohibited co-medication	Patient taking commercial cannabis or any cannabinoid medication during the trial.
26	Prohibited co-medication	Patient taking botulinum injection during the trial.
27	Prohibited co-medication	Initiation or changes in the dose of MS disease modifying therapy any time after randomization at Visit 2
28	Prohibited co-medication	Patient taking drugs solely metabolized by UGT1A9 and UGT2B7 during the trial
29	Prohibited co-medication	Patient taking strong CYP3A4 inducer during the trial
30	Prohibited co-medication	Initiation of a new course of physiotherapy any time after randomization at Visit 2
31	Prohibited co-medication	Patient changing dose or introducing antispasticity medication (baclofen, tizanidine, dantrolene)
32	Prohibited co-medication	Patient changing dose or introducing dalfampridine or fampridine

MS = Multiple sclerosis; MAS = Modified Ashworth Scale, IMP = Investigational Medicinal Product; IXRS = Interactive x Response System; LLMT-6 = Lower Limb Muscle Tone-6, LLMT-4 = Lower Limb Muscle Tone-6, PRN = pro re nata meaning as needed.

* Refers to important protocol which may or not be considered as major important deviation

Appendix 2 Clinical laboratory parameters

Biochemistry (Serum ¹)		Hematology (Whole Blood ¹)		Urinalysis (Urine ²)
Category	Parameters	Category	Parameters	Parameters
Hepatobiliary	Alanine aminotransferase	Red blood cells	Hematocrit	Blood
Hepatobiliary	Albumin	Red blood cells	Hemoglobin	Glucose
Hepatobiliary	Alkaline phosphatase	Red blood cells	Mean cell volume	Nitrites
Hepatobiliary	Aspartate aminotransferase	Red blood cells	Mean corpuscular hemoglobin	pH
Electrolytes and proteins	Calcium	Coagulation parameter	Platelets	Protein
Renal	Creatinine	Red blood cells	Red blood cell count	White blood cells
Hepatobiliary	Gamma-glutamyl transferase	White blood cells parameters	White blood cell count with automated differential	Specific gravity
Electrolytes and proteins	Potassium			Ketones
Electrolytes and proteins	Sodium			Urobilinogen
Hepatobiliary	Total bilirubin			Bilirubin
Electrolytes and proteins	Total protein			
Renal	Urea (blood urea nitrogen)			
Coagulation parameters	Prothrombin time (plasma ⁴)			

¹Analyzed at a central laboratory.

²Analyzed at the trial site by use of a dipstick (if allowed per local regulations).

³The standard drugs of abuse screen, including THC, will be analyzed by use of a urine dipstick at Visits 1 and 2. Patients will undergo a separate blood THC test at Visit 1 only.

⁴Analyzed at Screening (Visit 1) only.

Appendix 3 Unscheduled Clinical laboratory parameters

Biochemistry (Serum ¹)		Hematology (Whole Blood ¹)		Urinalysis (Urine ²)
Category	Parameters	Category	Parameters	Parameters
Hepatobiliary	Alanine aminotransferase	Red blood cells	Hematocrit	Blood
Hepatobiliary	Albumin	Red blood cells	Hemoglobin	Glucose
Hepatobiliary	Alkaline phosphatase	Red blood cells	Mean cell volume	Nitrites
Hepatobiliary	Aspartate aminotransferase	Red blood cells	Mean corpuscular hemoglobin	pH
Electrolytes, proteins and creatinine kinase	Calcium	Coagulation parameter	Platelet count	Protein
Renal	Creatinine	Red blood cells	Red blood cell count	White blood cells
Hepatobiliary	Gamma-glutamyl transferase	White blood cells parameters	White blood cell count	Specific gravity
Electrolytes, proteins and creatinine kinase	Potassium	White blood cells parameters	Total neutrophil count	Ketones
Electrolytes, proteins and creatinine kinase	Sodium	White blood cells parameters	Monocyte count	Urobilinogen
Hepatobiliary	Total bilirubin	White blood cells parameters	Lymphocyte count	Bilirubin
Electrolytes, proteins and creatinine kinase	Total protein	White blood cells parameters	Basophil count	Squamous epithelial cells
Renal	Urea (blood urea nitrogen)	White blood cells parameters	Eosinophil count	Mucus
Coagulation parameters	Prothrombin time (plasma4)			Microscopy
Hepatobiliary	Amylase			Leucocyte esterase
Electrolytes, proteins and creatinine kinase	chloride			Color
Electrolytes, proteins and creatinine kinase	Bicarbonate			Appearance
Lipids	HDL-Cholesterol			Bacteria

Biochemistry (Serum¹)		Hematology (Whole Blood¹)		Urinalysis (Urine²)
Lipids	LDL-Cholesterol			
Lipids	Total Cholesterol			
Lipids	Triglycerides			
Hepatobiliary	Lipase			
Electrolytes and proteins	Magnesium			
Electrolytes, proteins and creatinine kinase	Phosphorus			
Renal	Creatinine clearance			
Endocrinology	Insulin-like growth factor-1			
Endocrinology	Prolactin			
Renal	Estimate glomerular filtration rate			
Coagulation	INR			
Endocrinology	Glucose			
Electrolytes, proteins and creatinine kinase	Creatinine Kinase			
Immunology	HBsAg			
Immunology	HCV			
Immunology	HIV			

Appendix 4 Toxicity Criteria for Laboratory Hematology and coagulation Parameters based on CTCAE version 5.0

Laboratory Toxicity	Grade 1	Grade 2	Grade 3	Grade 4
Hematology				
Anemia (Hemoglobin Decreased)	<LLN – 6.2 mmol/L <LLN - 100 g/L <LLN – 10.0 g/L	<6.2 – 4.9 mmol/L <100 - 80 g/L <10.0 to 80.0 g/dL	<4.9 mmol/L <80 g/L <8.0 g/dL	
Hemoglobin increased	Increase in >0 - 2 g/dL	Increase in >2 - 4 g/dL	Increase in >4 g/dL	
White Blood Cells Decreased	<LLN – 3000/mm3 <LLN – 3.0 x 109/L	<3000 - 2000/mm3 <3.0 – 2.0 x 109/L	<2000 - 1000/mm3 <2.0 – 1.0 x 109/L	<1000/mm3 <1.0 x 109/L
Neutrophils count Decreased	<LLN – 1500/mm3 <LLN – 1.5 x 109/L	<1500 - 1000/mm3 <1.5 – 1.0 x 109/L	<1000 - 500/mm3 <1.0 – 0.5 x 109/L	<500/mm3 <0.5 x 109/L
Lymphocytes count Decreased	<LLN – 800/mm3 <LLN – 0.8 x 109/L	<800 – 500/mm3 <0.8 – 0.5 x 109/L	<500 - 200/mm3 <0.5 – 0.2 x 109/L	<200/mm3 < 0.2 x 109/L
Lymphocyte count increased		>4000/mm3-20,000/mm3 >4 - 20 x 109/L	>20,000/mm3 > 20 x 109/L	
Platelets count Decreased	<LLN – 75,000/mm3 <LLN – 75.0 x 109/L	<75,000 – 50,000/mm3 <75.0 – 50.0 x 109/L	<50,000 – 25,000/mm3 <50.0 – 25.0 x 109/L	<25,000/mm3 <25.0 x 109/L
Activated partial thromboplastin time prolonged (aPTT)	>ULN – 1.5 x ULN	>1.5 – 2.5 x ULN	>2.5 ULN °	

Appendix 5 Toxicity Criteria for Laboratory Biochemistry Parameters based on CTCAE version 5.0

Laboratory Toxicity	Grade 1	Grade 2	Grade 3	Grade 4
Chemistry				
Sodium Increased (Hypernatremia)	>ULN - 150 mmol/L	>150 - 155 mmol/L	>155 - 160 mmol/L	>160 mmol/L
Sodium Decreased (Hyponatremia)	<LLN - 130 mmol/L		<130 - 120 mmol/L	<120 mmol/L
Potassium Increased (Hyperkaliemia)	>ULN - 5.5 mmol/L	>5.5 - 6.0 mmol/L	>6.0 - 7.0 mmol/L	>7.0 mmol/L;
Potassium Decreased (Hypokaliemia)	<LLN - 3.0 mmol/L	<LLN - 3.0 mmol/L	<3.0 - 2.5 mmol/L	<2.5 mmol/L
Calcium Increased (Hypercalcemia)	>ULN - 11.5 mg/dL; >ULN - 2.9 mmol/L Ionized calcium >ULN - 1.5 mmol/L	>11.5 - 12.5 mg/dL; >2.9 - 3.1 mmol/L Ionized calcium >1.5 - 1.6 mmol/L	>12.5 - 13.5 mg/dL; >3.1 - 3.4 mmol/L; Ionized calcium >1.6 - 1.8 mmol/L	>13.5 mg/dL; >3.4 mmol/L; Ionized calcium >1.8 mmol/L
Calcium Decreased (Hypocalcemia)	<LLN - 8.0 mg/dL; <LLN - 2.0 mmol/L; Ionized calcium <ULN - 1.0 mmol/L	<8.0 - 7.0 mg/dL; <2.0 - 1.75 mmol/L Ionized calcium <1.0 - 0.9 mmol/L	<7.0 - 6.0 mg/dL; <1.75 - 1.5 mmol/L; Ionized calcium <0.9-0.8 mmol/L	<6.0 mg/dL; <1.5 mmol/L; Ionized calcium <0.8 mmol/L
Albumin Decreased (hypoalbuminemia)	<LLN - 3 g/dL; <LLN - 30 g/L	<3 - 2 g/dL; <30 - 20 g/L	<2 g/dL; <20 g/L	
Alkaline Phosphatase increased	>ULN - 2.5 x ULN if baseline normal 2.0 - 2.50 x baseline if baseline abnormal	>2.5 - 5.0 x ULN if baseline normal >2.5 - 5.0 x baseline if baseline abnormal	>5.0 - 20.0 x ULN if baseline normal >5.0 - 20.0 x baseline if baseline abnormal	>20.0 x ULN if baseline normal 20.0 x baseline if baseline abnormal
Alanine amino transferase increased	>ULN - 3.0 x ULN if baseline normal 1.5 - 3.0 x baseline if baseline abnormal	>3.0 - 5.0 ULN if baseline normal >3.0 - 5.0 x baseline if baseline abnormal	>5.0 - 20.0 x ULN if baseline normal >5.0 - 20.0 x baseline if baseline abnormal	>20.0 x ULN if baseline normal > 20.0 x baseline if baseline abnormal
Aspartate amino transferase increased	>ULN - 3.0 x ULN if baseline normal 1.5 - 3.0 x baseline if baseline abnormal	> 3.0 - 5.0 ULN if baseline normal >3.0 - 5.0 x baseline if baseline abnormal	>5.0 - 20.0 x ULN if baseline normal >5.0 - 20.0 x baseline if baseline abnormal	>20.0 x ULN if baseline normal > 20.0 x baseline if baseline abnormal
Blood Bilirubin Increased	>ULN - 1.5 x ULN if baseline normal >1.0-1.50 x baseline if baseline abnormal	>1.5 - 3.0 x ULN if baseline normal >1.5-3.0 x baseline if baseline abnormal	>3.0 - 10.0 x ULN if baseline normal >3.0- 10.0 x baseline if baseline abnormal	>10.0 x ULN if baseline normal > 10.0 x baseline if baseline abnormal
Gamma Glutamyl Transferase Increased	>ULN - 2.5 x ULN if baseline normal 2.0 - 2.5 x baseline if baseline abnormal	>2.5 - 5.0 x ULN if baseline normal >2.5 - 5.0 x baseline if baseline abnormal	>5.0 - 20.0 x ULN if baseline normal >5.0 - 20.0 x baseline if baseline abnormal	>20.0 x ULN if baseline normal >20.0 x ULN if baseline abnormal
Creatinine Increased	>ULN - 1.5 x ULN	>1.5 - 3.0 x baseline; >1.5 - 3.0 x ULN	>3.0 baseline; >3.0 - 6.0 x ULN	>6.0 x ULN

Chronic Kidney Disease	eGFR (estimated Glomerular Filtration Rate) or CrCl (creatinine clearance) <LLN - 60 ml/min/1.73 m ² or proteinuria 2+ present; urine protein/creatinine >0.5	eGFR or CrCl 59 - 30 ml/min/1.73 m ²	eGFR or CrCl 29 - 15 ml/min/1.73 m ²	eGFR or CrCl <15 ml/min/1.73 m ²
Hypoalbuminemia	<LLN - 3 g/dL; <LLN - 30 g/L	<3 - 2 g/dL; <30 - 20 g/L	<2 g/dL; <20 g/L	
Proteinuria	1+ proteinuria	2+ and 3+ proteinuria	4+ proteinuria	

Appendix 6 Abnormality Criteria

Hepatic abnormality criteria		
Hepatic laboratory Parameters	Abnormality criteria	
ALT	> 3 x ULN	
	>5 x ULN	
	> 8 x ULN	
	> 10 x ULN	
	> 20 x ULN	
AST	> 3 x ULN	
	>5 x ULN	
	> 8 x ULN	
	> 10 x ULN	
	> 20 x ULN	
ALP	> 1.5 x ULN	
	> 2 x ULN	
	> 3 x ULN	
Total bilirubin	> 1.5 x ULN	
	> 2 x ULN	
	> 3 x ULN	
	> 5 x ULN	
GGT	> 1 x ULN	
Blood pressures and pulse rate abnormality criteria		
Blood pressures and pulse rate criteria	Abnormality criterion value	Abnormality criterion on change from baseline
SBP	> 180 mmHg	≥ 20 mmHg increase from baseline

	< 90 mmHg	≥ 20 mmHg decrease from baseline
DBP	> 105 mmHg	≥ 15 mmHg increase from baseline
	< 50 mmHg	≥ 15 mmHg decrease from baseline
Pulse rate	> 120 bpm	≥ 10 bpm increase from baseline
	< 50 bpm	≥ 10 bpm decrease from baseline

Weight Abnormality Criteria

Weight criteria	Abnormality criteria
Weight (kg)	≥ 7% increase from baseline
	≥ 7% decrease from baseline

ECG abnormality criteria

ECG criteria	Abnormality criteria
QTcF interval prolongation*	> 450 msec
	> 480 msec
	> 500 msec
Change from baseline in QTcF interval*	> 30 msec increase from baseline
	> 60 msec increase from baseline
PR interval	< 120 msec
	> 200 msec
QRS complex	< 80 msec
	> 120 msec
HR	< 60 bpm
	> 100 bpm

ALT = alanine aminotransferase; AST = aspartate aminotransferase; ALP = alkaline phosphatase;
 GGT= gamma-glutamyl transferase; SBP = Systolic blood pressure; DBP = diastolic blood pressure;
 bpm=beats per minutes to be classified as potentially clinically significant, the measurement must
 satisfy both criteria: the criterion for the value and the criterion for the change relative to baseline.

*Abnormal QTcF interval categories as defined in ICH Guidelines E14

Any patients fulfilling at least one ECG abnormality criteria (as described in Appendix 6) or having at least one abnormal ECG assessed as significant by the investigator will be listed presenting all his/her ECG information.

Appendix 7 Prohibited medication solely metabolized by UGT1A9 and UGT2B7 and determination criteria

Examples of medications that are solely metabolized by UGT1A9 and UGT2B7 and prohibited for the duration of the trial are provided below.

Medications solely metabolized by UGT1A9		Medications solely metabolized by UGT2B7		
Medication name	ATC code	Medication name	ATC code	Comments
Flavopiridol		Benoxyprofen	M01AE06	
Propofol	N01AX10	Carbamazepine	N03AF01	
		Codeine	R05DA12 R05DA04 N02AJ01 N02AJ02 N02AJ03 N02AJ07 N02AJ08 N02AJ09 N02AA08 N02AA58 N02AA59 N02AA79	
		Cyclosporin A	L04AD01, S01XA18	
		Epirubicin	L01DB03	
		Indomethacin	C01EB03 M01AB01 M01AB51 M02AA23 S01BC01 S01CC02	S01CC02 also contains anti-infective medications
		Tacrolimus	D11AH01 L04AD02	
		Tiaprofenic acid	M01AE11	
		Zaltoprofen		Not popped up in ATC code list.
		Zomepirac	M01AB04	
		Zidovudine	J05AF01	

			J05AR01 J05AR04 J05AR05	Combination product Combination product Combination product
--	--	--	-------------------------------	---

ATC = Anatomic Therapeutic Class

Appendix 8 Prohibited medications strong CYP3A4 inducers and determination criteria

Strong CYP3A4 inducers		
Medication name	ATC code	Comments
Rifampicin	J04AB02 J04AB03 J04AM02 J04AM05 J04AM06 J04AM07 A07AA13* D06AX15* S01AA16* S02AA12*	This is a list on rifampicin only but also on products which contain rifampicin * refers to rifamycin
carbamazepine	N03AF01	
phenytoin	N03AB02 N03AB04 N03AB05 N03AB52	
phenobarbital,	N03AA01 N03AA02	
Primidone	N03AA03	
St John's Wort (hypericum perforatum)		Not popped up in ATC code list.

ATC = Anatomic Therapeutic Class

Appendix 9 Other Prohibited medications and determination criteria

Other prohibited medication			
Medication name	ATC code	Verbatim code	Comments
Nabiximols, cannabis or cannabinoid-based derived product	N03AX24 N02BG10		N03AX24: group of other anti-epileptics and cannabidiol is one of them This is the greater group of analgesics, and N02BG10 is a cannabinoid
Botulinum toxin injections,	M03AX01	Contains: ‘BO’ and ‘Tox’ “Dysport ‘Xeomin	Muscle relaxant products
Antipsychotic medications,	N05A apart from N05AN (Lithium) Including N05AH02 (BDZ)		
Benzodiazepines (if not following protocol requirements)	N03AE N05BA N05CD M03BX07		N03AE: clonazepam N05BA: broader group of anxiolytics contain the main used BDZ N05CD broader group of hypnotics but also contains melatonin for instance. M03BX07: tetrazepam

BDZ=Benzodiazepines

Appendix 10 Medications used in MS and determination criteria

Any medication used for MS along with its category will be retrieved from the eCRF Concomitant medication form. However, the information in the table below will be used to define subcategory of interest.

MS medications type	WHO-DD Therapeutic class	Standardized Medication name	ATC code	Verbatim term	Comments
Antispasticity medication	Muscle relaxant (M03)	Baclofen	M03BX01	Contains: 
“BACLOFEN”	
		Tizanidine	M03BX02	Contains: 
“TIZANIDINE”	
		Dantrolene	M03CA	Contains: 
‘DANTROLENE’	
		Tetrazepam (BDZ)	M03BX07		Not considered as a BDZ in the coding of ATC, but as a centrally acting muscle relaxant.
		Botulinum toxin	M03AX01	Contains: 
‘BO’ and ‘Tox’DysportXeomin	
	Antiepileptic (N03)	Others	M03B and M03C apart those mentioned above		Refers to the broader group of muscle relaxants
		Clonazepam	N03AE		N03AE is a BDZ
		Gabapentin	N03AX12		
		Pregabalin	N03AX16		
	Psychoanaleptic (N05)	Cannabinidiol	N03AX24		Not allowed per protocol
		Clozapine (BDZ)	N05AH02		
		Benzodiazepines	N05BA N05CD		N05BA and N05CD refers to a list of BDZ
Medication to treat other MS symptoms	Other system nervous system drug (N07)	Dalfampridine	N07XX007		
		Fampridine	N07XX007		

MS=Multiple sclerosis; ATC= Anatomic Therapeutic Class; BDZ=Benzodiazepines

Appendix 11 Adverse Drug Reaction of Special Interest – AE selections

Adverse drug of special interest type	AESI search
Falls and injuries	PT from either: SOC "Injury, Poisoning, and procedural complications" Accidents and injuries (SMQ) [20000135]
Drug reaction with eosinophilia and systemic systems (DRESS)	See Appendix 13
Disorientation and confusion	Confusion and disorientation High Level Term (HLT) [10010301]
Driving and road traffic accident	Impaired driving ability (PT) [10049564] Road traffic accident (PT) [10039203] Impaired ability to use machinery (PT) (10077474) Accident – for machinery (PT) (10000369)
Abuse liability	Drug abuse, dependence and withdrawal (SMQ) [20000100] Euphoric mood (PT) [10015535]
Abnormal liver adverse events	Drug related hepatic disorders – comprehensive search (SMQ) [20000006] Drug related hepatic disorders – severe events only (SMQ) [20000007]
Somnolence and sedation	Somnolence (PT) [10041349] Hypersomnia (PT) [10020765] Sedation (PT) [10039897]
Fatigue and lethargy	Fatigue (PT) [10016256] Lethargy (PT) [10024264]
Suicidal ideation and behavior	Suicide/self-injury (SMQ) [20000037] AEs will also be searched using the following search term string of suicidality-related terms (Bangs, 2008): accident, asphyxiation, burn, cut, drown, firearm, die, dying, gas, gun, hang, hung, immolat, injur, jump, attempt, kill, monoxide, mutilate, overdos, poison, self-damag, self-harm, self injur, shoot, slash, suffocation, and suic.
Significant cardiovascular (CVD) disease	Cardiac arrhythmias (SMQ) [20000049] Cardiac failure (SMQ) [20000004] Cardiomyopathy (SMQ) [20000150] Hypertension (SMQ) [20000147] Ischaemic heart disease (SMQ) [20000043] Pulmonary hypertension (SMQ) [20000130]
Cognitive function	Cognitive and attention disorders and disturbances High Level Group Term (HLGT) [10009841]
Depression and depressed mood	Depression (excl. suicide and self-injury) (SMQ) [20000167]
Psychosis and psychotic disorders	Psychosis and psychotic disorders (SMQ) [20000117] Disturbances in thinking and perception (HGLT) [1001351]
Seizures	Convulsions (SMQ) [20000079] (includes Seizure [PT]) [10039906]

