12.7.2.3 Adverse Events of Special Interest

An adverse events of special interest (AESI) is any adverse event of scientific or medical interest to the study medication. The types of AESIs which will be analyzed are presented in **Descriptive presentations of AESIs** will be given for each AESI category on the safety analysis set presenting:

- The number and percentage of patients with at least one treatment-emergent AESI,
- The number and percentage of patients with at least one treatment-emergent AESI by SOC and PT,
- The number and percentage of patients with at least one severe treatment-emergent AESI,
- The number and percentage of patient with at least one serious treatment-emergent AESI,
- The number of and percentage of patients with at least one treatment-emergent AESI leading to permanent IMP discontinuation,
- The number of treatment-emergent AESI,
- The number of severe treatment-emergent AESI,
- The number of serious treatment-emergent AESI,
- The number of treatment-emergent AESI leading to permanent IMP discontinuation,
- The number of unique* treatment-emergent AESI,
- The number of unique* severe treatment-emergent AESI,
- The number of unique* serious treatment-emergent AESI,
- The number of unique* treatment-emergent AESI leading to permanent IMP discontinuation,
- The time to first onset of treatment-emergent AESI categorized as :1-7 day, 8 to 14 days, 15 to 21 days, 21 to 28 days and > 28 days (as described in [Section 10.21.3](#)),

**Unique AESI is defined as any AESI coded with the same PT and having the same date of onset.*

Analysis of time to first onset of AESIs will be conducted by actual treatment arm on the Safety Analysis SAS using the SAS® LIFEEST procedure.

Assuming no carry over effect, Kaplan-Meier plots (estimates) of cumulative incidence of first onset of AESI will be provided by actual treatment arm on the Safety analysis set. The time to AESI onset (in days) is defined as the number of days from 1st IMP intake of the treatment arm (e.g., nabiximols, placebo) the AESI is emergent to (as defined in [Section 12.7.1](#)) until the onset of the AESI (see detailed in [Section 10.21.4](#)).

For patients not known to have experienced an AESI during respectively Period 1 and Period 2:

- Period 1 censoring day is the date of 1st IMP intake during Period 2 minus 1 day for those patients continuing in Period 2 and, the end of study date for those patients who discontinued before Period 2,

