- Period 2 censoring day is the end of study date in the period.

Additionally, for lost to follow-up patients:

- Period 1 censoring day is the earliest date between end of study date in the period and the planned Visit 6 day minus 1 day (Day 30),
- Period 2 censoring day is the earliest date between end of study date in the period and the planned Visit 10 day (Day 58).

To accompany the Kaplan-Meier (KM) plots, summary tables will display the KM estimates of cumulative probabilities (with 95% CI calculated based on the Greenwood method when applicable).

- of patients with an event at a specific time point such as 7, 14, 21, 28 (if applicable) days after 1st IMP intake in the studied period;
- time to first event based on the 10th, 20th, 30th, 40th, 50th (median) and 75th percentiles.

If the estimate of lower bound of the 95% CI is below '0' or the estimate of the upper bound of the 95% CI is over '1', then it will be respectively restricted to '0' and '1'.

The number of patients at risk along with the number and percentage of patients censored and with an event, using the number of patients at risk as denominator to calculate the percentage will also be displayed.

Each Kaplan-Meier plot (estimates) will only be provided if more than 5 patients are presenting an event in each treatment arm.

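### The suicidality AESI adds a 28-string partial-word text search with no stated field, matching rule or review of hits, so unrelated events can be counted as suicidality

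*SAP*

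**What the plan says.** SAP Appendix 11 is the table that defines each AESI category by its search criteria. The suicidality row names the suicide/self-injury SMQ and then adds: "AEs will also be searched using the following search term string of suicidality-related terms". The strings run from "accident, asphyxiation, burn, cut, drown, firearm, die, dying, gas, gun, hang, hung, immolat, injur, jump, attempt" to "kill, monoxide, mutilate, overdos, poison, self-damag, self-harm, self injur, shoot, slash, suffocation, and suic", 28 in all, and are credited to a 2008 source that is not in the SAP's reference list (Section 13.0).

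SAP 12.7.2.3 says that descriptive presentations "will be given for each AESI category on the safety analysis set presenting" a series of counts, starting with "The number and percentage of patients with at least one treatment-emergent AESI" and going on to severe, serious and treatment-stopping events and time to first onset. Kaplan-Meier output follows, under a threshold: "Each Kaplan-Meier plot (estimates) will only be provided if more than 5 patients are presenting an event in each treatment arm". SAP 12.7.1.1 also puts AESIs into the overall adverse event summary.

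Two neighbouring rows of Appendix 11 share vocabulary with the string list. Falls and injuries are selected through "SOC 'Injury, Poisoning, and procedural complications' Accidents and injuries (SMQ) [20000135", and the driving row includes "Road traffic accident (PT) [10039203".

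**The concern.** A bare string list is a screening tool. It is meant to over-collect so that a reader can sort the yield. Here it stands in the column that defines category membership, and the SAP has no step between running the search and filling the tables. A programmer who follows the plan to the letter would count the hits.

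The outcome is a sensitive one. Protocol Section 10 requires IMP to be stopped for suicidal behavior or type 4 or 5 ideation, and Protocol Section 14 provides for no data safety monitoring committee. A by-arm suicidality table containing stomach complaints and road accidents could show a difference between nabiximols and placebo that has nothing to do with suicidality. It could also disagree with the C-SSRS results for no clinical reason.

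**Working it through.** The SAP states no figure to reproduce here. The check is whether the listed strings catch unrelated terms, and under which matching rule.

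**Step 1: which rule does the list imply?** *Immolat*, *injur*, *overdos*, *self-damag*, *self injur* and *suic* are not complete words. Whole-word matching would make them useless, so some partial-word matching is intended. All six are cut at the right-hand end, so start-of-word matching is enough for them to work. Matching anywhere in a word is possible but not stated.

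**Step 2: apply the 28 strings, ignoring case, under three rules.**

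| Term | Source | Anywhere in word | Start of word | Whole word |
|---|---|---|---|---|
| Gastritis | SAP App. 13.2 | *gas* | *gas* | none |
| Vasculitis gastrointestinal | SAP App. 13.2 | *gas* | *gas* | none |
| Hepatocellular injury | SAP App. 13.2 | *injur* | *injur* | none |
| Road traffic accident | SAP App. 11 | *accident* | *accident* | *accident* |
| Hepatitis acute | SAP App. 13.2 | *cut* | none | none |
| Acute interstitial pneumonitis | SAP App. 13.2 | *cut* | none | none |
| Gastroenteritis | illustrative | *gas* | *gas* | none |
| Heartburn | illustrative | *burn* | none | none |
| Mood change | illustrative | *hang* | none | none |
| Fall | illustrative | none | none | none |
| Accidental fall | illustrative | *accident* | *accident* | none |

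The first four terms come from the SAP's own appendices and are caught even under start-of-word matching. Whole-word matching removes most false hits but disables the stems. None of the three rules makes the list both functional and specific without a review.

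**Step 3: is there a filter elsewhere in the SAP?** None was found in Appendix 11, the AESI section, the general adverse event section or the C-SSRS section. The SAP is more exact about other text searches:

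- SAP 10.21.2 (COVID-19 events) names the fields, the string and an excluded term.
- Appendices 9 and 10 state that the verbatim term must contain given text.
- Appendix 13.1 says when a word may appear anywhere in a preferred term.
- Appendix 1 refers one kind of deviation to the medical monitor.

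The suicidality row has none of these.

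**Step 4: size per false hit.** SAP 8.2 plans 68 completers, each exposed to both treatments, so take about 68 patients at risk per arm. One patient with a false hit adds 1/68 = 1.5 percentage points; at an assumed 70 exposed patients it would be 1/70 = 1.4. More than 5 patients per arm, the Kaplan-Meier threshold, means at least 6, or 6/68 = 8.8% of an arm.

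**Step 5: which outputs move?** The suicidality category counts and time-to-onset output can move. The overall AESI counts move only for events that are not already an AESI in another category. Gastritis could be such an event. Road traffic accident could not, because the driving row already selects it.

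**The case against.** The strongest reply is that the SAP only says events will be searched and never that every hit is counted. The cited method may include a review, and the sentence introducing the AESI types in SAP 12.7.2.3 breaks off in the available text, so its silence should be read with care. This stands in part. Automatic counting is the literal reading of Appendix 11 together with 12.7.2.3, but it is not an explicit instruction.

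Second, false hits would be visible. Each AESI category is also tabulated by SOC and PT, and AESIs are listed with the investigator's term, so gastritis would appear as gastritis. This stands and limits the harm, but the headline count and percentage would still be wrong.

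Third, suicidality is measured directly by the C-SSRS, with its own analyses in SAP 12.7.5.3 that the search does not touch. This also stands. A reader might infer that false hits could bury a real signal. The documents do not support that, because a real event would still appear by PT and could also be picked up by the SMQ and the C-SSRS.

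Two further inferences go too far. One is that any fall becomes a suicidality event: a plain *Fall* matches no string, and only a term that also contains *accident* or *injur* does. The other is that *acute*, *heartburn* or *change* terms are certainly caught: that needs matching anywhere in a word, which the SAP does not state.

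Finally, overlap between categories is not an error in itself, since one event may belong to two. The problem is membership of the suicidality category without any suicidal content.

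**Conclusion.** The point holds in this form: the selection rule for the suicidality AESI, applied as written, can count unrelated events, and the SAP has no stated field, matching rule, exclusion list or review to prevent it. Gastritis, hepatocellular injury and road traffic accident are caught under the stricter of the two partial-word rules; terms with *acute* are caught only under the looser one.

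The number of false hits is unknown in advance. Each affected patient shifts an arm's rate by about 1.5 percentage points, assuming about 68 exposed per arm. The effect is confined to the descriptive AESI tables, the overall AESI counts and the AESI Kaplan-Meier output. No tested hypothesis, efficacy result or C-SSRS analysis depends on it. The conclusion rests on partial-word matching, which the stems require, and on hits being counted, which is the literal but not the explicit reading. It is worth correcting before unblinding because the category is sensitive and the correction is cheap.

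**What to change.** Keep both the SMQ and the string search; dropping the strings and counting from the SMQ alone is not needed. In Appendix 11:

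- name the field searched (verbatim term, preferred term or both) and the matching rule (start of word or anywhere);
- state that string hits are candidates only;
- have the existing medical monitor review the candidates blinded to treatment, and document the outcome before unblinding. The data review meeting before database lock in SAP 12.4 is a natural point for this.

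In SAP 12.7.2.3, count only SMQ hits and confirmed string hits in this category, and show the two on separate lines.

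The cost is a few lines of SAP text, one blinded listing and a short review. No data collection changes.
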